6.4.2. Activities performed by sponsor representatives

Sponsor (Clinical Manager or a representative hereof) is responsible for:

- Training of investigator and study personnel in the informed consent procedure, study procedures, how to use the products, complete the CRF, how to report possible safety issues and in ISO 14 155. All training will be documented by site
- Support during the recruitment process and conduct of the investigation
- Monitoring
- Perform the interviews

6.4.3. Foreseeable factors that may compromise the outcome / results

No foreseeable factors are expected to compromise the outcome/results of the design.

6.4.4. Flow-chart

Table 4 chart showing the connection between visits and assessments.

	PERFORMED BY	SOURCE	INFORMATION AND INCLUSION VISIT 0	VISIT 1-3	VISIT 5-6	TERMINATION VISIT
General						
Oral information	Investigator	NA	X			
Written informed consent	Subject	Informed consent form	X			
Signed Letter of authority	Investigator	Letter of Authority Form	X			
Consent to interview	Subject	Informed consent form - Interview	X			
Check of in- and exclusion criteria	Investigator	CRF	X			
Allocation to subject number	Investigator	CRF	X			
Randomisation	Investigator	Randomisation Envelope	X			
Insurance of subjects well-being and compliance with CIP	Investigator	CRF	X	X	X	X
Registration of Demographic						
Date of birth	Investigator	CRF	X			
Check for symptoms of UTI, damage to urine tract system and use of analgesics before catheterisation						
Urine sample from subject	Subject	NA		X	X	
Leukocytes (urine dipstick)	Investigator	CRF		X	X	
Nitrite (urine dipstick)	Investigator	CRF		X	X	
Haematuria – microscopic (urine dipstick - erythrocytes)	Investigator	CRF		X	X	
Check for use of analgesics 24 hours before catheterisation	Investigator	CRF		X	X	
Catheterisation per randomisation	Investigator	CRF		X	X	
Registration/measurement of primary end points – during catheterisation						
Urine flow rate - Max flow ($\frac{ml}{s}$) - Middle flow ($\frac{ml}{s}$)	Investigator	CRF (or possible printed graph)		X	X	
Registration/measurement of secondary end points - after catheterisation						
Post void residual urine	Investigator	CRF (or possible print)		X	X	
Haematuria – macroscopic (visible blood)	Investigator	CRF		X	X	
Urine sample from subject	Subject	NA		X	X	
Haematuria – microscopic (urine dipstick)	Investigator	CRF		X	X	
AEs/ADEs/SAEs/SADEs	Investigator	CRF		X	X	X
Registration of explorative end points						
Overall discomfort during catheterisation	Subject	CRF		X	X	X
Discomfort during insertion	Subject	CRF		X	X	

Discomfort during withdrawal	Subject	CRF		X	X	
Discomfort during urination post catheterisation	Subject	CRF		X	X	
Handling during insertion	Investigator	CRF		X	X	
Handling during withdrawal	Investigator	CRF		X	X	
Handling during insertion	Investigator	CRF		X	X	
Handling during catheterisation	Investigator	CRF		X	X	
Interview	Coloplast representative	Interview notes		V3	V6	
Urine flow - Micturition time (sec) - Flow time (sec) [REDACTED] - Micturition volume (ml)	Investigator	CRF (or possible printed graph)		X	X	
Registration of termination						
Termination form. Completed	Investigator	CRF				X

Investigator can delegate tasks to trained study personnel. This will be documented by the Delegation Log and Training Log.

6.4.5. Randomisation Procedure

At the inclusion visit each subject will be allocated randomly into to one of the possible catheterisations orders for the first four catheterisations and then again into one of two possible catheterisation orders for the last two catheterisations. Subjects are allocated to a randomisation number per a randomisation list generated automatically by computer (SAS). The investigator or a representative hereof opens a sealed, non-transparent envelope with the randomisation block inside. Randomisation number is registered in the CRF by investigator or a representative. The randomisation list is archived in Sponsor File.

6.4.6. Blinding

During the investigation, the subject will be blinded with a curtain so he will not be able to see which catheter is used. The nurse is not blinded as it is not possible to blind the products due to visible differences. It is a disadvantage that it is not possible to blind the nurses as there could be some bias in their assessment of the products tested. However, it is the subject who assesses the secondary end points regarding discomfort (VAS) during catheterisation and micturition.

6.4.7. Case Report Forms

All assessments and observations throughout the investigation for each subject must be carefully recorded in the CRF. The CRFs are printed and supplied by Sponsor. A CRF is provided for each subject. It is the responsibility of the Investigator that all data are entered promptly and correctly. Each CRF have printed instructions for completion.

The CRF for each subject will be divided in two parts; one for the investigator or representative to complete (Investigator Binder) and one for the subjects two complete (Subject Binder). The study personnel will be responsible for guiding the subject on how to complete the subject's part of the CRF. The CRF will clearly state which parts are to be completed by whom. The subject's part will be the pages regarding discomfort during insertion and withdrawal of the catheter measured by the VAS-scale. These pages will be in Danish. After

completion by subject, the study nurse or investigator will measure the VAS-scale and write the measurement in the CRF.

The sponsor will be responsible for training the investigator and the investigation personnel in completion of the CRF. Only personnel who have signed the Site Personnel Signature and Delegation Log and the Clinical Investigation Training Log will fill in the Investigator Binder.

It will be the responsibility of investigator that all measurements and observations are correctly noted with a pen (permanent writing utensil) in the CRF.

Any correction in the CRF must be clearly signed and dated by authorised site personnel. The entry corrected must be crossed out so that the entry is still legible.

Example 1:

2010-11 PLN

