6.1.2. Discussion of clinical investigation design

This study is a single blinded, randomised, crossover study divided into two parts, with healthy subjects.

A cross-over design has been chosen over a parallel design due to minimisation of interpersonal variation. Only blinding of subjects is possible, since nurses will catheterise and since there is a visual difference in the products. A lower number of subjects are required with this study design as each subject act as his own control.

Healthy subjects have been chosen since discomfort must be evaluated by subjects with normal uréthral sensation. As this is an exploratory study no formal sample size calculation has been performed. However, it is assumed that ten subjects will be adequate for obtaining indications on performance and acceptance.

During the investigation, there must be a minimum of five days between each visit/catheterisation to allow potential micro trauma from the catheterisations to heal.

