Subject is asked about symptoms for urinary tract infections (frequent urination, stinging or pain at urination) and use of analgetica up to 24 hours prior to the visit. In addition, a urine sample is made and microscopic haematuria, nitrite and leukocytes is measured before catheterisation to further ensure no symptoms of urinary tract infection or damage to the urinary tract system. If negative for these symptoms, use of analgetica and microscopic haematuria/nitrite/leukocytes, the subject will be catheterised with the randomised product and urine flow rate is measured. Hereafter the bladder is scanned for post void residual urine, by using a hand held bladderscanner, [REDACTED]. The subject is offered something to drink and after 1-2 hours a urine sample is made and microscopic haematuria measured. Subject and nurse register relevant answers in CRF, including possible adverse events. In addition, subject register the end points regarding discomfort (VAS-scale) and the nurse register the assessments in the CRF. Next visit is scheduled.

If subjects have agreed to participate in interviews, Test Visit 3 will be prolonged to include interview.

Test Visit (V5-V6) – approximately two hours

Subject is asked about symptoms for urinary tract infections (frequent urination, stinging or pain at urination) and use of analgetica up to 24 hours prior to the visit. In addition, a urine sample is made and microscopic haematuria, nitrite and leukocytes is measured before catheterisation to further ensure no symptoms of urinary

tract infection or damage to the urinary tract system. If negative for these symptoms, use of analgetica and microscopic haematuria/leukocytes/nitrite, the subject will be catheterised with the randomised product [REDACTED] [REDACTED] and urine flow rate is measured. Hereafter the bladder is scanned for post void residual urine, by using a hand held bladderscanner, [REDACTED]. The subject is offered something to drink and after 1-2 hours a urine sample is made and microscopic haematuria measured. Subject and nurse register relevant answers in CRF, including possible adverse events. In addition, subject register the end points regarding discomfort (VAS-scale) and the nurse register the assessments in the CRF. Next visit is scheduled.

If subjects have agreed to participate in interviews, Test Visit 6 will be prolonged to include interview. At the end of Test Visit 6 the termination page in CRF is completed by nurse.

Interview – plus one hour

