8.1. Data review, database cleaning, and issuing and resolving data queries

Data management and statistical analyses is carried out by Medical Affairs, Coloplast A/S.

To ensure correct data entry, data is entered twice (double data entry). Data management is responsible for control of data consistency and for completeness of data from each subject.

Discrepancies are listed in Data Query Forms (DQF), and the Investigator is responsible for solving these promptly. When all DQFs are solved the database is locked and the statistical analyses are performed.

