12.4. Financial conditions

The investigation is initiated and sponsored by Coloplast A/S.

Coloplast pays the salary for the clinical staff in Denmark and for all investigation materials. The investigation expenses are expected to amount [REDACTED] per subject. The investigator is employed by Coloplast A/S, thus a Disclosure of Conflicts of Interests will be filled out before initiation of the investigation. An external nurse will be in-sourced to conduct the visits together with Coloplast personnel.

Subjects will be paid for their participation in the study and receives a gift voucher equivalent in value to [REDACTED] per visit. The gift is taxable (B-tax) and the subjects is responsible for reporting this.

13. Informed consent process

Written informed consent is obtained from all subjects participating in the investigation after thorough written and verbal information. The information is given by the investigator or his/her representative in the subjects' native non-technical language. Each subject will be fully informed about the aim of the investigation, procedures, potential risks or inconveniences and/or expected benefits and have a minimum of 24 hours before deciding on participation. The subjects will be informed that their participation is voluntary and that they may leave the investigation at any time, without this having any influence on their further treatment.

The informed consent signature form includes personally dated signatures of the subject and the Investigator or a representative hereof responsible for conducting the informed consent process. A copy will be provided to the subject.

If new information is to be given during the investigation, sponsor will inform the investigators, and the new information is given to the subjects by the investigator. If new information becomes available that can significantly affect a subject's future health and medical care that information will be provided to the subject in written form. Clinical Manager is responsible for writing the information and providing it to investigators that will further provide it to the subjects. If applicable, all affected subjects shall be asked to confirm their continuing informed consent in writing.

This procedure also applies to informed consent obtained from a subject's legal representative. The procedure cannot waive the subjects' legal rights.

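### The blinded subject's discomfort (VAS) marks are turned into numbers by staff who can know the product, which leaves a small and avoidable risk of bias

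*Combined protocol and SAP*

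**What the plan says.** Subjects sit behind a curtain and mark a 10 cm line on four scales: overall, insertion, withdrawal, and urination afterwards (6.1.1, 6.4.6). On the staff, section 6.4.6 states: "The nurse is not blinded as it is not possible to blind the products due to visible differences". It accepts that this could bias the nurses' assessments and answers that discomfort is assessed by the subject.

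The number that reaches the database comes from a later step. Under section 6.4.7, once the subject has completed the page, "the study nurse or investigator will measure the VAS-scale and write the measurement in the CRF". The visit description in 6.4.1 agrees: "subject register the end points regarding discomfort (VAS-scale) and the nurse register the assessments in the CRF".

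Both possible readers can know the product. The nurse performs the catheterisation. On allocation, section 6.4.5 says: "The investigator or a representative hereof opens a sealed, non-transparent envelope with the randomisation block inside". Section 12.4 adds two facts about who these people are: "The investigator is employed by Coloplast A/S", and "An external nurse will be in-sourced to conduct the visits together with Coloplast personnel".

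The hypothesis in 5.2 includes the condition that overall discomfort does not get worse. Section 7.1 analyses the VAS values with the same type of mixed model as the primary endpoint.

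**The concern.** The argument in 6.4.6 depends on the discomfort result coming from someone who does not know the product. That is true of the mark. It is not true of the number, which is produced by a person whose possible bias the same section has just accepted. Section 6.4.6 does not mention this step.

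A reading or rounding habit that differs by product would pass straight into the treatment contrast, and a narrow confidence interval would not reveal it. For a no-worsening claim the awkward direction is a lean in favour of the prototypes, because it would hide a true increase of the same size. Blinding the nurse to the catheter is not possible. Having the nurse read the line is a choice.

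**Working it through.** **Is the reading step covered by another control?** Setting the sections side by side:

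- 6.4.6: the protection is that the blinded subject makes the assessment.
- 6.4.7 and 6.4.1: unblinded staff measure and record it. No second reader, resolution or rounding rule is given.
- 6.7: full verification is named for consent, eligibility and adverse events. VAS is not named.
- 8.1: double data entry checks that the written number is keyed correctly. It does not check the reading of the line.
- 6.7.1: the CRFs are source data, so the marked page is kept and could be re-measured. No re-measurement is planned.

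The step is therefore uncovered, although it can be checked afterwards.

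**How large could it be?** The documents give no VAS SD, effect size or power, so there is no planned figure to reproduce. What follows is an illustration for one Part A contrast.

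Inputs from the plan: 10 subjects, 3 visits in Part A, two-sided 5% level (6.1, 7.3). Assumptions: complete data, within-subject SD *s* of 0.5 to 2.0 cm, product-dependent reading shift *b* of 1, 2 or 5 mm, and no true difference.

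- Residual df = 30 − 1 − 9 (subjects) − 2 (treatment) − 2 (visit) = 16, so t = 2.12. Age varies between subjects and takes no within-subject df.
- SE of a contrast = s × √(2/10). For s = 1.0 cm it is 0.447 cm; for s = 2.0 cm it is 0.894 cm.
- 95% CI half-width = 2.12 × SE, which is 0.95 cm and 1.90 cm.
- A 2 mm shift as a share of the half-width: 0.2/0.95 = 21% and 0.2/1.90 = 10.5%.
- The false-positive rate is the two-sided rejection rate of a noncentral t with 16 df and noncentrality b/SE. For 2 mm the noncentrality is 0.2/0.447 = 0.45 and 0.2/0.894 = 0.22.

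| Within-subject SD (cm) | Half-width (cm) | 2 mm as share of half-width | False-positive rate, 1 mm | 2 mm | 5 mm |
|---|---|---|---|---|---|
| 0.5 | 0.47 | 42% | 7.0% | 13.4% | 55.6% |
| 1.0 | 0.95 | 21% | 5.5% | 7.0% | 18.3% |
| 1.5 | 1.42 | 14% | 5.2% | 5.9% | 10.8% |
| 2.0 | 1.90 | 10.5% | 5.1% | 5.5% | 8.2% |

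Shifts of 1 to 2 mm matter little unless the within-subject SD is near 0.5 cm. A 5 mm shift would matter more, but should be plain to anyone who re-measured the pages.

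One contrast on overall discomfort rests on 20 marks (10 subjects × 2 products).

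**The case against.** The judgement of discomfort remains the blinded subject's. What is left to staff is measuring a length on a 10 cm line. Section 6.4.7 asks for permanent pen and for signed, dated corrections that leave the old entry legible, and the page is retained. Nothing in the documents suggests that anyone would lean towards the prototypes. The study is exploratory with no success criteria (7.5), so no decision rule depends on this result. Discomfort is listed as explorative in the synopsis and 6.1.1, although 6.4.6 and 7.1 treat it as secondary; those labels should be reconciled. All of this stands, and it keeps the point small.

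Three stronger readings are tempting, and the documents do not support them:

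- A reader might infer that the blinding of discomfort is defeated. It is not, because the mark is made blind and can be re-read.
- A reader might infer that VAS is the only outcome the blinding protects. VAS is four scales, and adverse events are registered by subject and nurse together (6.4.1), so they too draw partly on the blinded subject.
- A reader might infer that sponsor employees produce the numbers. Employment by the sponsor is stated for the investigator. The visit nurse is external and in-sourced, although working alongside sponsor personnel.

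A practical objection also has force. Data management sits in the sponsor's Medical Affairs (8.1), section 6.7.1 gives those staff access to all CRFs, and the randomisation number is written in the CRF (6.4.5). Data-entry staff are therefore not unaware of product by default, and handing them the ruler helps only if the order of work is controlled.

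Finally, 6.4.7 has study personnel guide the subject in completing the page. Influence on the mark itself could not be detected later, and that route is arguably the more important one. It is a separate exposure and does not close this one.

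**Conclusion.** The point holds as a minor one. The plan relies on blinded marks but lets people who can know the product convert them into the analysed values, and no planned check re-reads the mark. That is an avoidable risk of bias, not evidence of bias.

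Under an assumed 2 mm lean and an assumed within-subject SD of 1.0 to 2.0 cm, the contrast moves by about 21% to 10% of its 95% CI half-width, and the false-positive rate rises from 5% to between 7.0% and 5.5%. Neither the lean nor the SD comes from the documents. With 10 subjects, imprecision is much the larger problem. The case for changing the procedure is that the change is cheap, not that the likely distortion is large.

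**What to change.** Amend 6.4.7 so that the analysed VAS value is measured from the retained Subject Binder pages by the existing data-entry staff at the double-entry step, before they open the Investigator Binder or the randomisation list for that subject. The text should state that:

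- the subject pages carry only subject and visit number;
- all four scales are covered, since 6.4.7 names only insertion and withdrawal as subject pages while 6.4.4 has the subject complete all four;
- the two entries are independent readings at a stated resolution;
- disagreements are resolved by re-measuring the mark while still unaware of product;
- any value noted at the visit is not used in the analysis.

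Cost: the five visit days listed in 7.1 give 10 × 5 × 4 = 200 marks, or 400 readings. At an assumed half minute each, that is 200 minutes, or a little over three hours. VAS values arrive slightly later, and the order of data entry has to be controlled and documented because 6.7.1 opens all CRFs to sponsor staff. No visit, procedure or subject burden changes.

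This does not address the guidance given to subjects. A fixed, neutral instruction text in the same edit would help there.

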07 JAN 2011
Day Month Year
Ex AUG

Example 2:

No Yes
2010-11 PLN

Figure 4 Two examples of how to make corrections in the CRF

The investigator will keep a separate list with the subject ID numbers, names and addresses in a locked room. Only data referred to in this clinical investigation plan will be recorded in the CRFs.

The completed CRFs will be collected ongoing after monitoring.

6.5. Concomitant treatment

Healthy subjects may not use analgesics 24 hours prior to catheterisation visits, see inclusion criteria. Subjects may not participate in other clinical investigations related to urinary tract system during this investigation.

6.6. Supplementary materials and equipment

Supplementing devices or instruments normally used for catheterisation (e.g. medical gloves, tray for urine collection), the uroflow meter and equipment for ultrasound measurements are supplied by Sponsor.

The intermittent catheters [REDACTED] used in the investigation will be supplied by Sponsor. For bladder scanning, a hand held [REDACTED] will be used. The bladder scanner will be supplied by Sponsor.

6.7. Monitoring Plan

During the period of the investigation monitoring is planned and carried out by the Clinical Manager.

Before doing any review of subject data, the Clinical Manager must review the signed Informed Consent Form(s) and only monitor data from subjects with a correct signed Informed Consent Form.

The first monitoring visit (Mon 1) at the site should be conducted as soon as reasonably possible after the first subject at the site has completed the first visit of the investigation to minimise systematic errors done by site.

Additional monitoring will be conducted in accordance to the recruitment rate:

- Monitoring visit two (Mon 2) will be conducted as soon as possible after the first five subjects have completed Part A.
- Monitoring visit three (Mon 3) will be conducted as soon as possible after the first five subjects have completed the investigation.
- Monitoring visit four (Mon 4) will be completed as soon as possible after the last subject has completed the investigation
- Monitoring visit five, Close out visit, will be conducted as soon as possible after database lock

Written informed consent, in- and exclusion criteria and all Adverse events occurring in the investigation will be 100% verified for timely completion for all subjects enrolled in the investigation.

Investigation Site File shall be monitored for 100% completion per the Investigation File Requirement Checklist. Monitoring activities conducted by the clinical manager will be documented in the site visit report applicable to the conducted visit. A summary describing the observation(s) and actions required shall be provided as soon as reasonably possible to the investigator after the conducted monitoring visit. The sponsor representative will have close contact to the site in the recruitment period to ensure that any concerns, problems or recruitment challenges are solved with the site in a timely manner.

